1.4.1. Contraindications, Warnings and Precautions

The following Contraindications, Warnings and Precautions apply:

Contraindications: Animal reproductive studies have not been conducted with GSK2816126. Therefore, the compound must not be administered to pregnant women or nursing mothers.

Safety and efficacy in the paediatric populations has not been investigated, therefore, GSK2816126 should not be administered to children.

Any known hypersensitivity to agents structurally similar to GSK2816126 or the constituents of the vehicle would contraindicate GSK2816126 use.

Warnings: GSK2816126 is intended for investigational use only by selected investigators familiar with the information in this Protocol and experienced in conducting clinical studies.

GSK2816126 may only be administered to human subjects participating in clinical studies sponsored/approved by GSK and who have provided formal written consent.

Precautions: ECG monitoring for evidence of QTc prolongation must be conducted. Co-administration of medications that are known to prolong the QT interval and have a risk of causing TdP are to be avoided beginning **14 days** prior to the first dose of study drug or longer if necessary, as determined by the primary investigator or medical monitor until discontinuation from the study. Co-administration of medications that are known to prolong the QT interval and have a possible risk of causing TdP are to be used with caution. Subjects will be instructed to minimize or avoid prolonged exposure to natural or artificial sunlight (e.g., tanning beds, sunlamps, UVA or UVB treatments) and wear loose fitting clothing with long sleeves, sunglasses, and broad rim hat that protect the skin from sun exposure AND use a broad spectrum sunscreen (e.g., UVA and UVB protective with minimum SPF 30) on any uncovered areas of the body if outdoors from the time of first dose of study medication until at least 2 weeks (14 days) following last dose of study medication due to long elimination phase.

Potential for Abuse and Dependence: Not Known

Overdosage: There is no specific antidote for overdose with GSK2816126. In the event of a suspected overdose, it is recommended that the appropriate supportive clinical care should be instituted, as dictated by the subjects' clinical status.

2. OBJECTIVES, ENDPOINTS AND HYPOTHESES

2.1. Part 1: Phase I Dose Escalation

Part 1 Objectives		Part 1 Endpoints
Primary	
 To determine the safety and tolerability, and establish the recommended Phase 2 dose (RP2D) of IV administered GSK2816126 	
 Adverse Events (AEs), Serious Adverse Events (SAEs), Dose Limiting Toxicity (DLT), withdrawals due to AEs, dose interruptions and reductions, and changes in safety assessments (e.g., clinical laboratory parameters, vital signs, and cardiac parameters)
Secondary	
 To describe the pharmacokinetics of GSK2816126 after single- and repeated administration 	
 GSK2816126 PK parameters following single- (Day 1) and repeat-dose administration of GSK2816126, including area under the concentration-time curve (AUC), pre-dose (trough) concentration at the end of the dosing interval (C_{τ}), maximum observed concentration (Cmax), time of occurrence of Cmax (tmax), terminal phase half-life (t_{1/2}), time

Part 1 Objectives		Part 1 Endpoints
	
 • To evaluate the relationship between GSK2816126 exposure and safety/efficacy/PD parameters • To determine clinical activity of GSK2816126 in GCB DLBCL and solid tumors containing EZH2 inhibitor sensitizing mutations or prostate cancer 	invariance and accumulation ratio 
 • GSK2816126 exposure markers (dose, concentration, Cmax or AUC) and safety/efficacy/PD responses. PD response assessed by change from baseline in tri-methylation of Histone H3K27 (H3K27me3) • Best Overall Response rate (complete response [CR] + partial response [PR])
Exploratory	
 • To confirm tumor EZH2 and GCB-DLBCL status • To investigate the mechanism of action of GSK2816126 • To identify biomarkers predictive of response or resistance to GSK2816126 	
 • Immunohistochemistry (IHC) for confirmation of GCB-DLBCL status • PCR or NGS to determine EZH2 mutation status • Evaluate transcriptional and/or protein changes upon GSK2816126 treatment • Correlate baseline tumor genomic [deoxyribonucleic acid (DNA)], protein and/or transcription [ribonucleic acid (RNA)] profiles with response
Hypothesis	
No formal statistical hypotheses are being tested for the dose escalation in Part 1. Analysis of the data obtained from dose escalation of Part 1 will utilize descriptive methods only.
 
The cohort expansion of GCB-DLBCL patients in Part 1 will assess the overall response rate (p) of GCB-DLBCL patients. The null and alternative hypotheses for the overall response rate are detailed below:
 
The null hypothesis is:
 
$H_0: p \leq 20\%$
	

Part 1 Objectives	Part 1 Endpoints

The alternative hypothesis is:
 
$H_A: p \geq 40\%$
 
For cohort expansion of solid tumor subjects in Part 1, there is no formal statistical hypothesis being tested. Analysis of the data obtained from solid tumor expansion cohort will utilize descriptive methods only.
	

[figure not shown]
2.2. Part 2: Expansion

		Part 2 Objectives	Part 2 Endpoints
Primary	
 To determine clinical activity of GSK2816126 in cohorts of subjects with EZH2 mutant and wild type GCB-DLBCL and tFL and subjects with MM 	
 Overall response rate (% of subjects achieving CR and PR per response criteria) 	
Secondary	
 To determine the safety, tolerability of the selected IV dose of GSK2816126 To characterize the population PK of GSK2816126 To evaluate the relationship between GSK2816126 exposure and PD parameters To generate samples (data reported separately) with which to characterize the metabolic profile of GSK2816126 after repeat-dosing (In the PK/PD expansion cohort only) To determine the amount of GSK2816126 excreted in urine after dosing at steady state To generate samples (data reported separately) with which to investigate the potential for GSK2816126 to affect cytochrome P450 (CYP) 3A4 enzyme activity 	
 AEs, SAEs, DLTs, withdrawals due to AEs, dose interruptions and reductions, and changes in safety assessments (e.g., clinical laboratory parameters, vital signs, and cardiac parameters) Population PK parameters for GSK2816126 including clearance (CL), and volume of distribution (Vd) and relevant covariates which may influence exposure (e.g. age, weight, or disease related covariates) GSK2816126 exposure markers (dose, concentration, Cmax or AUC) and PD responses. PD response assessed by change from baseline in tri-methylation of Histone H3K27 (H3K27me3) Samples to characterize the metabolites in blood, bile and/or urine Concentration of GSK2816126 in urine measured with an investigational bio-analytical method and extrapolated to total amount excreted in urine over time using urine volume Samples to assess a potential change in 4b-OH cholesterol to cholesterol ratio in plasma following repeat dosing of GSK2816126 (data reported separately) GSK2816126 exposure markers (e.g. dose, concentration, Cmax, or AUC) and safety/efficacy/ responses 	

		Part 2 Objectives	Part 2 Endpoints
		
 • To evaluate the relationship between exposure and safety/efficacy parameters • To begin to characterize the durability of response and progression free survival with GSK2816126 	
 • Duration of response (DoR) • Progression-free survival (PFS)
Exploratory		
 • To identify biomarkers predictive of response or resistance to GSK2816126 • To investigate the mechanism of action of GSK2816126 • To investigate the relationship between genetic variants in candidate genes and the pharmacokinetics (PK) and safety profile of GSK2816126 based on Part 1 and 2 data combined 	
 • Evaluation of wild-type (WT) subject tumors for the presence of additional, undefined, mutations in the EZH2 gene • Correlate baseline tumor genomic (DNA), protein and/or transcription (RNA) profiles with response • Evaluate transcriptional and/or protein changes upon GSK2816126 treatment • Pharmacogenomic (PGx) analysis of whole blood
Hypothesis	
In Part 2, the overall response rate (p) of GCB-DLBCL and tFL patients will be assessed for each EZH2 mutation status cohort (wild type and mutant), and also for MM patients.
 
 • For each of the GCB-DLBCL and tFL cohort, the null and alternative hypotheses of the overall response rate are as following: 
The null hypothesis is:
 $H_0: p \leq 20\%$ 
The alternative hypothesis is:
 $H_A: p \geq 40\%$ 
 • For MM cohort: 
The null hypothesis is:
 $H_0: p \leq 10\%$ 
The alternative hypothesis is:
 $H_A: p \geq 25\%$		

3. INVESTIGATIONAL PLAN

3.1. Study Schematic

3.2. Discussion of Study Design

Protocol waivers or exemptions are not allowed. Therefore, adherence to the study design requirements, including those specified in the Time and Events Table (Section 7.1), are essential.

Supplementary study conduct information not mandated to be present in this protocol is provided in the accompanying Study Procedures Manual (SPM). The SPM will provide the site personnel with administrative and detailed technical information that does not impact subject safety.

This is a Phase I, open-label, multiple-dose, multicenter, dose-escalation, first-time-in-human study conducted in two parts. In Part 1, an accelerated dose titration will be employed with one subject per dose level until the first instance of a \geq Grade 2 drug related non-hematological toxicity or dose limiting toxicity (DLT) (Section 3.3.3) occurs. Exceptions for pre-specified Grade 3 non-serious non-hematological drug related adverse events that would allow continuation of accelerated dose escalation are listed in Section 3.3.1.

In the accelerated dose escalation cohorts and the 3+3 dose escalation cohorts, the dose will be escalated based on all available data, including PK data, the safety information from prior cohorts, as well as the recommended dose from a Continuous Reassessment Method [Neuenschwander-Continuous Reassessment Method (N-CRM)] analysis [Neuenschwander, 2008]. The N-CRM is a type of Bayesian adaptive dose-escalation scheme. The method is fully adaptive and makes use of all the DLT information available at the time of each dose assignment. The Fixed and Adaptive Clinical Trial Simulator (FACTS) will be used to conduct the N-CRM analysis. The DLT information

on all subjects enrolled in the trial is used to update the estimated dose-toxicity relationship and to provide supportive information in addition to the 3+3 design in the next escalation/de-escalation decision.

After the accelerated dose titration, subjects will be enrolled in a standard 3+3 dose escalation design. Dose escalation will continue until a recommended Phase 2 dose (RP2D) is determined or until a maximum tolerated dose (MTD) or a dose of 3000 mg twice-weekly is reached. Any dose level during Part 1 dose escalation may be expanded up to 12 subjects to explore safety and preliminary efficacy. At MTD/RP2D the cohort may be expanded to enroll approximately 27 GCB-DLBCL subjects and approximately 15 subjects with solid tumors containing EZH2-sensitive mutations or prostate cancer to explore additional safety and preliminary efficacy. Based on results of the Part 1 analysis in totality, Part 2 expansion cohorts may be opened and subjects will be assigned to cohorts based on disease and EZH2 mutation status.

Safety assessments will be performed weekly for the first 4 weeks and then at regular intervals as outlined in the Time and Events Table (Section [7.1](#)).

Disease response in lymphoma and solid tumor subjects will be assessed as described in the T&E table (Section [7.1](#)).

Futility and Efficacy analysis will be performed on GCB-DLBCL subjects enrolled at the MTD/RP2D in cohort expansion of Part 1 as listed in Section [12.2.1.2](#).

3.3. Part 1: Dose-Escalation Phase

3.3.1. Accelerated Dose Escalation

Initially, an accelerated dose titration scheme will be used starting with a dose of 50 mg [[Simon, 1997](#)]. Evaluation of at least one subject who has completed one cycle of treatment is required prior to determining the dose for the next cohort, with one cycle being defined as twice weekly dosing for three weeks and one week off. In the absence of Grade 2 or higher non-hematologic toxicity (described in Section [3.3.2.1](#)) or a Dose Limiting Toxicity (DLT) (described in Section [3.3.3](#)), subsequent cohorts will allow up to 100% dose escalations up to 500 mg (approximately 1/6th of the dog HNSTD).

Subsequent dose escalation steps would be up to a maximum of 50% at each step ([Table 1](#)). Following the initial occurrence of a Grade 2 toxicity or DLT in a subject during the first cycle (within 28 days of dose 1), accelerated titration will transition to a standard 3+3 dose escalation.

Table 1 Dose Titration Procedures

Dose Level	Toxicity in Study	Increase in Dose
Accelerated Dose Titration Phase		
Dose Level -1		Lower doses may be used if Dose Level 1 exposure is significantly higher than predicted or if there is excessive toxicity. This may be achieved by reducing the dose or by alternate dosing schedules
Dose Level 1		Starting Dose: 50 mg
Subsequent Dose Levels	No subjects with a \geq Grade 2 toxicity (exceptions below in Section 3.3.2.1) or DLT (Section 3.3.3)	Increase by \leq 100% increase in dose up to 500 mg, \leq 50% increase in dose thereafter (No subjects with \geq Grade 2 drug related toxicity AND no subjects with any DLTs in first 28 days of treatment)
End of Accelerated Dose Titration Phase	One subject \geq Grade 2 drug related non-hematological toxicity in the first 28 days of treatment) or \geq Grade 3 drug related specific toxicity (See Section 3.3.2.1)	Begin 3+3 dose escalation phase (note that once 3+3 phase is initiated, the procedure may revert to the accelerated dose titration phase – see criteria below in Reverting to Accelerated Dose Titration)

3.3.2. 3+3 Dose Escalation Phase

Two additional subjects will be enrolled to the dose level at which accelerated dose titration ends, for a total of at least 3 subjects at that dose level. If no DLTs are observed in any of the 3 subjects, then dosing will proceed to the next higher dose level (\leq 100% increase in dose up to 500 mg, \leq 50% increase in dose thereafter). An additional three subjects will be enrolled at this dose level if 1 of 3 subjects experiences a DLT. Subjects will be entered in a staggered approach with at least 7 days between each subject to minimize the risk of inadvertently exceeding the maximum tolerated dose in multiple subjects. Dose escalation decisions will be made as outlined in Table 1. Escalation to the next dose level will not increase greater than 2 fold from the previous dose level up to a dose of 500 mg. Subsequent dose escalation steps would be up to a maximum of 50% at each step. If 2 or more DLTs are observed at any dose level, the MTD will have been exceeded.

An evaluable subject in Table 2 is defined as a subject who has been on study for at least 28 days (one cycle). Evaluation of safety data from at least 1 subject during the accelerated dose titration or at least 3 subjects in the standard dose titration who have completed 28 days of dosing on study (one cycle) is required prior to defining a new dose and starting the next cohort. Once a higher dose has been cleared, subjects at lower dose levels who remain on study drug and have not experienced dose limiting toxicity will be allowed to escalate up to that level.

In the accelerated dose escalation cohorts and the 3+3 dose escalation cohorts, the dose will be escalated based on all available data, including PK data and the safety profile of prior cohorts, as well as the recommended dose from the N-CRM analysis described in Section 12.

Table 2 3 + 3 Dose Escalation Design

Number of Subjects with DLT in a Cohort	Action
0 out of 3 subjects	Escalate to the next dose level with increase $\leq 100\%$ up to 500 mg, $\leq 50\%$ thereafter if none of the subjects have Grade 2 toxicity (in the first 4 weeks of treatment)
	Escalate to next dose level with an increase of $\leq 50\%$ if (in the first 4 weeks of treatment) there has been: - One or more subjects with Grade 2 toxicity
1 out of 3 subjects	Accrue 3 additional evaluable subjects at current dose level for a total of 6 evaluable subjects
1 out of 6 subjects	Escalate to the next dose level with an increase of $\leq 50\%$
2 or more subjects in a dosing cohort (up to 6 subjects)	MTD has been exceeded. Either evaluate an intermediate dose lower than current dose or expand a prior cohort up to 12 subjects

Reverting from 3+3 Dose Escalation to Accelerated Dose Titration: Once Grade 2 toxicity is seen in one subject, there are 2 scenarios where the accelerated dose escalation may be resumed.

- 1) If two additional subjects are added at the dose where Grade 2 toxicity was seen in the initial subject and if no Grade 2 or higher toxicity is seen in either of the 2 new subjects, the accelerated dose escalation may be resumed, or
- 2) If the 3+3 method is used and, at the next higher dose, the 3 subjects do not have a grade 2 or higher toxicity, the accelerated dose escalation may be resumed.
(Before any decision is made to reinitiate accelerated dose titration a discussion between the investigators and the GSK medical monitor is required)

3.3.2.1. Toxicity Leading to Termination of Accelerated Titration

The following events will result in an end to accelerated dose escalation:

- Any Grade 2 or higher adverse event that is considered related to the study medication except for alopecia, drug-related Grade 3 fatigue, or asthenia; diarrhea, nausea, and/or vomiting that respond to standard medical care within 48hrs; or Grade 3 or higher electrolyte abnormalities unrelated to underlying malignancy and corrected within 48 hrs
- Grade 2 QT interval corrected for heart rate prolongation (confirmed on triplicate ECGs by manual reading)
- Grade 2 alanine aminotransferase (ALT) increase (unless clearly attributed to the underlying disease)
- Any grade adverse events that are considered in the judgment of the investigator and GSK Medical Monitor to be serious and related to the drug and requiring additional subjects to better understand the toxicity

3.3.3. Dose Limiting Toxicity

Dose-limiting toxicity (DLT): An event will be considered a DLT if it occurs within the first 4 weeks (28 days) of treatment and meets one of the following criteria (Table 3 [NCI-CTCAE, 2009]) unless it can be clearly established that the event is unrelated to treatment.

Table 3 Dose-Limiting Toxicity Criteria

Toxicity	DLT Definition
Hematologic	
 Grade 4 absolute neutrophil count (ANC) for >7 days Febrile neutropenia (according to CTCAE v.4.0 criteria) Grade 4 thrombocytopenia or anemia for >7 days
Non-hematologic	
 Grade 3 or greater nausea, vomiting, or diarrhea that does not respond to standard medical care within 48 hours Grade 3 or greater clinically significant non-hematologic toxicity per national cancer institute - common terminology criteria for adverse events (NCI-CTCAE), v 4.0
Infusion reactions	
 Infusion reactions will not be considered a DLT unless a \geqgrade 3 reaction recurs after administration of optimal prophylaxis
Other	
 Inability to receive >75% of scheduled doses in treatment period due to toxicity Grade 2 or higher toxicity that does not meet the above definitions but, in the judgment of the investigator and GSK medical monitor, is dose limiting Grade 2 or higher toxicity which occurs beyond 28 days which in the judgment of the investigator and GSK Medical Monitor is considered to be a DLT

3.3.4. Maximum Tolerated Dose

The MTD will be exceeded if 2 or more subjects in a cohort of up to 6 subjects experience a DLT.

The RP2D will be determined based on the MTD or biologically active dose (example: clinical response), the safety profile, and available PD data generated from all subjects in Part 1. If necessary, alternate schedules can be explored to determine additional biologically active doses even after a RP2D is defined.

3.3.5. Intra-subject Dose Escalation

Intra-subject dose escalations may be considered on a case-by-case basis, provided that the subject has not experienced a \geq Grade 2 drug related non-hematological toxicity or DLT in the accelerated dose escalation phase (Section 3.3.1 and Section 3.3.3), or a DLT in the 3+3 dose escalation, and contingent upon one of the following:

- A higher dose level cohort has been cleared in either the accelerated dose titration phase or the 3+3 phase.

- If a dose level has been cleared and no subjects have been identified for enrollment at the next dose level, and after the subject has completed a minimum of 8 weeks of dosing on that regimen without a DLT, that subject may be escalated to the next higher dose level after review of all safety data, and approval by a GSK Medical Monitor. In this case, the subject must follow the dosing schedule outlined in the Time and Events Table (Section 7.1) (starting at Day 1) as he/she will be the first subject exposed to the higher dose level.

Decision on intra-subject dose escalation will be made after review of all safety data and approval by a GSK Medical Monitor and discussion with the investigator. In this case, the subject may begin dosing at the higher dose level as it will have already been demonstrated to be tolerable and monitoring will be performed as described in the protocol. Subjects approved for intra-subject dose escalation may require additional limited PK and/or PD sampling as determined by GSK Clinical Pharmacology. Additional safety assessments may be specified at the time of the dose escalation or schedule modification based on the safety profile in previous subjects at the higher dose level.

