	to 3000 mg/day, however, only a limited number of subjects have received GSK2816126.	clothing with long sleeves, sunglasses, and broad rim hat that protect the skin from sun exposure AND use a broad spectrum sunscreen (e.g., UVA and UVB protective with minimum SPF 30) on any uncovered areas of the body if outdoors from the time of first dose of study medication until at least 2 weeks (14 days) following last dose of study medication due to long elimination phase.
Hepatic Toxicity	
In first in human study EZH117208 (present study), an increase in level of ALT has been noted in the group of subjects receiving doses of 1800 mg to 3000 mg (single infusion dose). None of these ALT increases have been associated with increase in total bilirubin or INR and all have shown improvement following either withholding or discontinuing GSK2816126. The 3000 mg dose has been declared to exceed the MTD. The highest dose being explored in this study is 2400 mg .
 
In nonclinical species given GSK2816126, twice weekly for 2 and/or 4 weeks, changes in liver pathology (inflammation, hyperplasia) in dogs and clinical chemistry parameters (i.e. increases in ALT, AST, alkaline phosphatase (ALP), bilirubin and decreases in albumin) in rats and dogs were observed and were consistent with systemic inflammation. These effects were considered secondary to vascular damage at the infusion and/or surgical site and attributable to vascular or extravascular irritant (vesicant) effects of GSK2816126 and prolonged intravenous catheterization.
 
No current evidence suggests the presence of reactive metabolites. No glutathione conjugates were identified in the in vitro, ex vivo studies that were
	Dosing at 3000 mg has been discontinued, with the highest dose being explored is at 2400 mg. Continued laboratory and clinical monitoring for liver dysfunction (LFT, coagulation parameters INR/PTT, other blood chemistry, clinical observation for jaundice). Dose management and stopping criteria as per guidelines for non-hematologic toxicity (Section 3.8.3 and Table 4) and hepatic safety monitoring (Section 8.3.1)

Potential Risk of Clinical Significance	Data/Rationale for Risk	Mitigation Strategy

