3.3.6. Alternative Dosing Schedules

Alternative schedules may be evaluated based on emerging data. Less frequent dosing schedules (e.g., once weekly) may be implemented without an amendment if emerging data suggest that twice weekly administration will result in excessive toxicity or if PD data suggest less frequent administration may be warranted. In this case, the starting dose would be one dose level above the highest dose which has been determined to be tolerable when administered twice weekly. In addition, alternative dosing schedules which result in increased frequency of administration may be considered if the safety, PK, and PD data suggest that a sufficient therapeutic exposure cannot be achieved using the initial dosing schedule; this would require a protocol amendment. Dose escalation will continue using the guidelines outlined in [Table 2](#).

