3.8.3. Dose Adjustment for Non-Hematologic Toxicity

See [Table 4](#) Dose Adjustment Guideline for drug related non-hematologic toxicities based on worst grade.

Table 4 Dose Adjustment Guideline for Drug Related Non-Hematologic Toxicity

Worst Grade	Dose Adjustment
G1	No change in dose
G2	Continue dosing with no change OR Consider holding for up to 2 weeks for toxicity to resolve to baseline or \leq Grade 1, then continue at the same dose OR dose reduce to 1 dose level lower per dose escalation scheme if the toxicity is considered a DLT.
G3 and 4	Hold for up to 2 weeks for toxicity to resolve to baseline or \leq Grade 1, then dose reduce to 1 dose level lower per dose escalation scheme If no recovery to \leq Grade 1* or baseline after 14 days, patient should be withdrawn.

If the non-hematologic toxicity or event resolves to baseline or \leq Grade 1 within 14 days of stopping therapy, treatment with GSK2816126 may be restarted at 1 dose level lower than the current dose. For a non-DLT, the treatment with GSK2816126 could restart at a full dose, if deemed appropriate.

If the non-hematologic toxicity does not resolve to \leq Grade 1 or baseline within 14 days, the subject should be withdrawn from the treatment permanently (Section 6.3). However, if the investigator and GSK Medical Monitor agree that further treatment will benefit the subject, treatment can restart at 1 dose level lower and under weekly clinical monitoring. If the toxicity resolves to \leq Grade 1 or baseline, the dose may be resumed to the initial dose level.

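### Sections 3.3.2 and 3.3.5 set different toxicity conditions for moving a subject up to a cleared dose, and neither says which governs

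*Protocol*

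**What the plan says.** Two places in the protocol state when a subject already on treatment may move to a higher dose that has been cleared.

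- **Section 3.3.2 (3+3 Dose Escalation Phase):** "subjects at lower dose levels who remain on study drug and have not experienced dose limiting toxicity will be allowed to escalate" to the cleared level. The only toxicity condition is the absence of a DLT. The sentence just before it speaks of both the accelerated titration and the standard titration.
- **Section 3.3.5 (Intra-subject Dose Escalation):** escalation may be considered case by case. A subject is ineligible after "Grade 2 drug related non-hematological toxicity or DLT in the accelerated dose escalation phase" (Grade 2 or higher), or after a DLT in the 3+3 phase. One of the two qualifying situations is that a higher dose level has cleared, which is the situation in 3.3.2. The section adds: "Decision on intra-subject dose escalation will be made after review of all safety data and approval by a GSK Medical Monitor".

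Three other sections decide whether the two rules can diverge.

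- **Section 3.3.3, Table 3:** the default non-hematologic DLT is "Grade 3 or greater clinically significant non-hematologic toxicity per national cancer institute" criteria. A Grade 2 event is a DLT only if the investigator and Medical Monitor judge it so.
- **Section 3.3.2.1:** events that end acceleration include "Grade 2 alanine aminotransferase (ALT) increase (unless clearly attributed to the underlying disease").
- **Section 3.8.3, Table 4:** for Grade 2 toxicity the first options are "Continue dosing with no change OR Consider holding for up to 2 weeks for toxicity to resolve to baseline" or Grade 1 or less, then to continue at the same dose.

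**The concern.** A subject in the accelerated phase can have a drug-related Grade 2 non-hematological event, such as an ALT rise, that stops acceleration without being a DLT. Table 4 lets that subject stay on drug. When a higher dose later clears, 3.3.2 says the subject will be allowed to go up and 3.3.5 says the subject is not eligible.

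The sentence in 3.3.2 gives the less protective answer, for a subject who has already shown drug-related toxicity in a first-in-human study. Section 3.2 allows no waivers or exemptions, so a site acting on the permission in 3.3.2 would depart from 3.3.5. What is at stake is consistent dosing of individual subjects, not any estimate or test.

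**Working it through.** The protocol gives no figure on this point to reproduce. The check compares the two toxicity conditions case by case, assuming a higher dose has cleared and the subject is still on drug.

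| Phase in which the subject was treated | Worst relevant event | 3.3.2 | 3.3.5 |
|---|---|---|---|
| Accelerated | DLT | barred | barred |
| Accelerated | Related non-hematological, Grade 2 or higher, not a DLT | **allowed** | **barred** |
| Accelerated | Neither | allowed | may be considered |
| 3+3 | DLT | barred | barred |
| 3+3 | Grade 2 or higher, not a DLT | allowed | may be considered |
| 3+3 | Neither | allowed | may be considered |

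The toxicity conditions conflict only in the second row.

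**Can that row occur?** Yes. Section 3.3.2.1 expects Grade 2 events that end acceleration, Table 3 does not make them DLTs by default, and Table 4 permits continued dosing. Some Grade 3 events also fall in this row: nausea that responds to care within 48 hours, or a first infusion reaction, is not a DLT under Table 3.

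**Can the number be bounded?** No. Counting only the event that ends each accelerated run would give one subject per run, but this is not an upper limit. Table 1 ends a run on toxicity in the first 28 days, while the bar in 3.3.5 carries no such window, so a later Grade 2 event in an earlier accelerated subject also counts. Section 3.3.5 also does not repeat the exceptions in 3.3.2.1. They may carry over through its reference to 3.3.1, which would narrow the class, but the text does not say so.

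**Can the dose step be bounded?** Not usefully. The figures below are illustrative only.

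- One 50% step: 1.5 times.
- Two 50% steps: 1.5 × 1.5 = 2.25 times.
- Two 100% steps, if acceleration resumes and both stay within the 500 mg limit: 2 × 2 = 4 times.
- From 1800 mg to 2400 mg, the highest dose now being explored: 2400 / 1800 = 1.33 times.

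None of these is tied to a documented subject.

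**How much reach is left?** Little. Section 1.3.1 states: "The 3000 mg dose has been declared to exceed the MTD". Under 3.3.4, exceeding the MTD takes at least two subjects with a DLT in one cohort, so escalation had moved past single-subject cohorts. For alternative schedules, 3.3.6 says "Dose escalation will continue using the guidelines outlined in" Table 2, the 3+3 table, where the two sections agree. A return to acceleration remains formally possible under 3.3.2, after discussion with the Medical Monitor.

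**The case against.** The strongest reply is that the two sections can be applied together. The sentence in 3.3.2 is a permission inside a section on the 3+3 phase. Section 3.3.5 is the dedicated rule and sets conditions. Nothing in 3.3.2 requires escalation, so following 3.3.5 never breaches it. If 3.3.5 supplies the approval step for every intra-subject escalation, its eligibility clause should apply as well, and harm would need a Medical Monitor to approve under that section while overlooking its opening condition.

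Much of this stands. Treating 3.3.5 as governing is the sensible reading, and the approval step makes harm unlikely. It does not remove the inconsistency. The 3.3.2 paragraph covers both phases, so its heading does not limit it to 3+3 subjects. There is no cross-reference, and approval settles who decides, not which eligibility rule is applied.

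A reader might infer that 3.3.2 opens a route to a higher dose without Medical Monitor approval. The text does not support that: 3.3.2 is silent on approval, so the review and approval in 3.3.5 still apply. A reader might also infer that the sections conflict for 3+3 subjects. They do not, because both use the no-DLT condition there.

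**Conclusion.** The inconsistency is real and narrow. It is confined to accelerated-phase subjects with a drug-related non-hematological event of Grade 2 or higher that was not a DLT, who remain on drug below a cleared dose. Few subjects can meet that description, but neither their number nor their dose step can be bounded from the document, and the protocol does not show that one is on treatment now.

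The conclusion assumes that the 3.3.2 sentence applies to subjects from both phases, as its paragraph suggests. If the exceptions in 3.3.2.1 carry into 3.3.5, the class is slightly smaller but not empty.

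It would be wrong to infer any effect on the MTD, the RP2D, sample size, error rates or the response analyses; nothing in the two sections reaches those. Priority is low, on grounds of dosing-safety consistency.

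**What to change.** Keep Section 3.3.5 unchanged as the governing rule. Replace the sentence in 3.3.2 with one that defers to it, for example: *After a higher dose level has cleared, a subject still being treated at a lower level may be considered for escalation, subject to the eligibility and approval conditions of Section 3.3.5.*

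This removes the less protective permission and leaves the Medical Monitor with one eligibility rule. It adds no procedure, visit or data collection, and costs one sentence in the next amendment.
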